### Research Synopsis

Study title - Rapidly absorbing polyglactin 910 versus monocryl for laceration repair: a randomized trial

Study Population – recently postpartum women who delivered at Virginia Commonwealth University Labor and Delivery with a first or second degree laceration or episiotomy requiring repair

Study Design – Prospective, randomized

Sample Size – 400

Study Duration – 24 months

Primary Objective – dyspareunia

Secondary Objectives – perineal pain

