#### Objectives:

##### Primary Objective

To evaluate the rates of dyspareunia using a female sexual function index -6 survey with rapidly absorbing polyglactin 910 compared to monocryl.

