##### Secondary Objectives

To assess overall perineal pain using a pain scale.

To assess overall sexual function.

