#### Study design/methodology:

This randomized controlled trial will be conducted at VCU medical center comparing 2 types of suture: rapid polyglactin 910 (Vicryl Rapide) and monofilament (Monocryl) for first and second-degree lacerations or uncomplicated episiotomies requiring suture repair. Patients will be enrolled in the study immediately after vaginal delivery if a laceration occurs spontaneously or if episiotomy is performed. Patients will be randomized to one of the 2 sutures after enrollment. Inclusion criteria include English speaking, patients with first and second degree spontaneous lacerations or those with midline or mediolateral episiotomies that were uncomplicated, and hemodynamically stable patients. Exclusion criteria include non-english or Spanish speaking, women without laceration or with third or fourth degree lacerations.

Randomization will be obtained via computer generation in consecutively numbered, opaque sealed envelopes with the name of one of the suture materials. The envelope will be opened at the time of repair of perineal laceration once inclusion criteria have been met by the physician or midwife performing the laceration repair. Repair with the chosen suture will be performed using the continuous suture technique using a 3-0 suture. Various maternal and fetal characteristics will be recorded

including maternal age, gravity and parity, gestational age at delivery, birth weight, insurance type and race.

In the immediate postpartum time period while the patient is hospitalized, patients will be given ibuprofen 600 mg every 6 hours or oxycodone 5mg and acetaminophen 325mg every 4 hours as needed for pain. If sufficient pain control is not achieved with these medications, then morphine 4mg IV will be administered until appropriate pain control is satisfactory. They will also be give the standard prescriptions that are routinely dispensed to all postpartum patients including ibuprofen 600mg every 6 hours and oxycodone 5mg and acetaminophen 325mg every 4 hours to be used as needed.

Pain will be evaluated using a pain scale at 6 week telephone interview. At three months postpartum another telephone interview will be conducted and six questions of the Female Sexual Function Index will be asked.

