#### Statistical Analysis Plan:

A chi square analysis and Fisher's exact test will be used for data analysis.

A goal sample size of 400 patients will be included in the study. With 200 patients in each arm of the study and assuming a standard deviation of 1, with a 15% loss to follow up, we would be able to detect a difference in pain scores of 0.25 or more.

Patients will be excluded from analysis if they are lost to follow up after the repair. Attempts will be made to contact the patient via telephone. If the patient is lost to follow up after their 6 week visit, this data will be included in the analysis.

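### The sample size of 400 is justified only by a difference in pain scores; nothing shows what difference in the primary outcome, the dyspareunia rate, the trial can detect

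*Combined protocol and SAP*

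**What the plan says.** The Research Synopsis gives "Primary Objective – dyspareunia", and the Primary Objective is "To evaluate the rates of dyspareunia using a female sexual function index -6 survey". The timing is in the Study design/methodology section: "At three months postpartum another telephone interview will be conducted and six questions of the Female Sexual Function Index will be asked".

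Pain is secondary. The Secondary Objectives read "To assess overall perineal pain using a pain scale", and the design section adds "Pain will be evaluated using a pain scale at 6 week telephone interview".

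The only sample-size statement is in the Statistical Analysis Plan section. It takes 200 women per arm, "assuming a standard deviation of 1, with a 15% loss to follow up", and concludes that "we would be able to detect a difference in pain scores of 0.25 or more". It does not say which pain score or visit is meant, or which visit the 15% refers to. The tests named in the same section are chi-square and Fisher's exact. On later loss it says: "If the patient is lost to follow up after their 6 week visit, this data will be included in the analysis".

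**The concern.** The number enrolled rests on an outcome that is not the primary one. Sensitivity for a mean depends on its SD. Sensitivity for a rate depends on the rate itself, and the plan states none. The sizing also does not match the plan's own tests, which compare proportions.

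The practical risk lies in reading a null primary result. Without a planning rate and a detectable difference, nobody can tell from the plan whether such a result argues against an important difference between the sutures or only reflects too few women. The 0.25 figure may be taken as reassurance about dyspareunia, which it cannot give.

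**Working it through.** **Inputs from the plan (Statistical Analysis Plan section).** 200 per arm; 15% loss, so 200 × 0.85 = 170 per arm; SD 1; difference 0.25.

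**Assumptions of this review, not in the documents.** Two-sided 5% and 80% power, with variants shown; the 15% loss also applies at three months; starting dyspareunia rates of 10% to 50%.

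**1. The plan's own figure.** Detectable difference in means = (z_alpha + z_power) × SD × √(2/n).

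- 170 per arm, two-sided: (1.960 + 0.842) × √(2/170) = 2.802 × 0.1085 = 0.304.
- 200 per arm, two-sided: 2.802 × √(2/200) = 0.280.
- 170 per arm, one-sided 5%: 0.270.
- 200 per arm, one-sided 5%: 0.249.

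At 5% and 80% power, 0.25 appears only with a one-sided test and the stated 15% loss ignored. With 170 per arm, two-sided, power for 0.25 is Φ(0.25/0.1085 − 1.960) = 63.5% (63.2% by the t distribution). At 80% power, two-sided, 0.25 needs 2 × 2.802² / 0.25² = 251.2, so 252 evaluable per arm. With 170 per arm and 80% power it needs a one-sided alpha of about 0.07. Because alpha, sidedness and power are unstated, this is a failure to reproduce, not a proven arithmetic error.

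**2. The primary outcome.** For rates p1 and p2 with mean p̄,

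power = Φ{ [ |p1 − p2|√n − 1.960 √(2p̄(1 − p̄)) ] / √(p1(1 − p1) + p2(1 − p2)) }.

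Check at p1 = 0.20, p2 = 0.0929, n = 170: p̄ = 0.1465. The numerator is 0.1071 × 13.04 − 1.960 × 0.500 = 0.416, the denominator is 0.494, the ratio is 0.84, and power is 80%.

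Solving for p2 at 80% power, 170 per arm:

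| Rate in one arm | Detectable fall to | Detectable rise to |
|---|---|---|
| 10% | 2.6% | 21.0% |
| 20% | 9.3% | 33.4% |
| 30% | 17.1% | 44.6% |
| 40% | 25.8% | 55.1% |
| 50% | 35.0% | 65.0% |

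The falls run from 7.4 to 15.0 points and the rises from 11.0 to 15.1. Fisher's exact test needs a difference about 0.2 to 0.7 points larger.

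**3. Power for a 10-point fall, 170 per arm.** 73.5% from 20%, 56.8% from 30%, 48.9% from 40%, 45.7% from 50%.

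**4. Illustration of further loss.** If another 15% were lost between the two calls, 200 × 0.85 × 0.85 = 144.5, about 145 per arm. From 20%, the detectable fall is then to 8.5% and the rise to 34.6%. Across the five rates the limits move by 0.5 to 1.3 points.

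**5. Is there a planning rate in the documents?** The Background mentions 20%, but for lasting pain and dyspareunia together over the long term. It is at best a proxy for a three-month dyspareunia rate, and the sizing does not use it.

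**The case against.** The first defence is that the pain scores meant could be the pain item of the FSFI, which would tie the sizing to the primary instrument. That does not help: it would still be a difference in means, not in a rate.

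The second is that nothing here shows the trial to be too small. That stands. With no planning rate or target difference, 400 cannot be called inadequate; with no loss, 200 per arm gives 80.2% power for 20% against 10%. The defect is a missing justification for the primary outcome.

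The third is that the sizes above rest on supplied assumptions. That is true and unavoidable, since the plan states none. The table is also a best case: it takes all 170 women per arm as scoreable for dyspareunia, uses the chi-square approximation, and spends the full alpha once, although a mid-point analysis for safety is planned with no alpha rule. The 145-per-arm case is only an illustration.

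The fourth is that the missing FSFI-6 rule and the non-reproducing 0.25 are separate matters. They are, and the main point does not depend on the 0.25. The rule is still needed, because a rate cannot be sized until a case is defined. Chi-square and Fisher's exact test suit a dyspareunia rate; they clash only with the pain-score sizing.

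**Conclusion.** The concern holds and must be fixed. The stated sensitivity belongs to a secondary outcome, and no section sizes the primary one. That conclusion comes from the text alone and needs no assumption.

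The size of the gap does depend on assumptions. Under those listed above, the trial detects differences of roughly 7 to 15 percentage points, depending on the underlying rate and the direction. Under the same settings the pain claim is optimistic: about 0.30 rather than 0.25.

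**What to change.** In the Statistical Analysis Plan section, state alpha, sidedness and power, and replace the pain-score sentence. If the sponsor confirms two-sided 5% and 80% power, the text could read:

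> Dyspareunia is defined as [FSFI-6 rule]. With 200 women enrolled per arm and 15% assumed lost by the three-month call, 170 per arm are evaluable. At two-sided alpha 0.05 and 80% power, from a rate of [X%, with source] in one arm, the trial can detect a fall to [Y1%] or a rise to [Y2%] in the other. Fewer than 170 per arm may be evaluable because of further loss after six weeks or women who cannot be scored for dyspareunia.

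Y1 and Y2 come from the table. If no single X can be justified, print the whole table. If other settings were intended, state them and recompute. If outcome data have already been seen, X should come from an outside source and not from this trial.

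Once the pain score and visit are confirmed, keep pain as secondary:

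> For [pain score, visit], with SD 1, 170 per arm and two-sided 5%, the trial has 80% power for a difference of about 0.30 and about 63% power for 0.25.

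Report the primary result as a risk difference with a 95% confidence interval alongside the test. The interval shows what the data exclude, whatever planning rate is chosen.

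**Cost.** No extra patients. Most of this is wording, but the FSFI-6 rule defines the primary endpoint and so needs a decision by the sponsor, who must also supply the sourced rate and the intended alpha, sidedness and power. At the settings above, the stated sensitivity for pain will look less favourable.

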#### Informed Consent Process:

Informed consent will be obtained after delivery, prior to laceration repair.

#### Privacy and confidentiality:

Subject's names will be kept on a password protected database and will be linked only with a study identification number for this research. There are no patient identifiers. All data will be entered into a computer that is password protected.

Risk/Benefit:

Risk to participants: This study does not present any risks to the participants.

Benefits to Participants: This study does not present any direct benefit to the participants. However the study does provide an opportunity to gain a better understanding of suture material that can potentially minimize pain and dyspareunia that will benefit women undergoing vaginal delivery and laceration repair in years to come.

Data Safety Monitoring:

A mid-point statistical analysis will be performed to ensure patient safety

Conflict of Interest:

The principal and co-investigators have no conflicts of interest to report.

References:

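### The mid-point look is meant to protect patients, but no wound or other adverse event is listed as trial data, so neither it nor the final analysis would have wound-event counts by arm.

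*Combined protocol and SAP*

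**What the plan says.** Under Data Safety Monitoring, within the section Privacy and confidentiality, the combined protocol and SAP says: "A mid-point statistical analysis will be performed to ensure patient safety". It names no outcome for that analysis, no definition of mid-point, no reviewer and no consequence.

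Study design/methodology gives the follow-up data. At the first contact, "Pain will be evaluated using a pain scale at 6 week telephone interview". At the second, three months postpartum and again by telephone, "six questions of the Female Sexual Function Index will be asked". The other data are introduced by "Various maternal and fetal characteristics will be recorded", and the named items are age, gravidity and parity, gestational age, birth weight, insurance type and race. The objectives match: dyspareunia, perineal pain and overall sexual function.

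The Statistical Analysis Plan sets 400 patients, 200 per arm, "with a 15% loss to follow up", without saying when that loss occurs. On missing follow-up it says "Patients will be excluded from analysis if they are lost to follow up after the repair", and then "If the patient is lost to follow up after their 6 week visit, this data will be included in the analysis".

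**The concern.** A safety analysis needs safety data, and none is listed. The background gives reasons to want it. It says that suture left in too long may lead to wound infection and breakdown. It cites a review in which dehiscence and resuturing differed between synthetic suture and catgut, and another comparison in which suture removal differed between standard and rapidly absorbing suture. It gives absorption times of 42 days for the rapid material and 90 to 110 days for the monofilament, so the two arms differ on the property it connects with wound harm. It also says these two materials have not been compared before.

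If the arms do differ in wound problems, nothing the plan lists would record them by arm, at the mid-point or at the end. The trial would miss harm information that is cheap to collect. The primary dyspareunia comparison is not affected.

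**Working it through.** **Step 1: are the data there?** The plan gives no figure on this point to reproduce, so the check begins with the text.

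| Wound event | Where the document mentions it | Listed for collection? |
|---|---|---|
| Infection | Background | No |
| Breakdown or dehiscence | Background | No |
| Re-suturing | Background | No |
| Suture removal | Background | No |

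No other adverse event and no wound examination is listed either.

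**Step 2: how many women would the look have?** Inputs from the Statistical Analysis Plan are 400 patients, two equal arms and 15% loss. Two assumptions are needed: that mid-point means the first 200 randomised, and when the loss occurs.

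- All loss before the 6-week call: 400 × 0.5 × 0.85 / 2 = 85 per arm.
- No loss by then: 400 × 0.5 / 2 = 100 per arm.
- At the end: 400 × 0.85 / 2 = 170 per arm.

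**Step 3: what could a test show if the events were collected?** The documents give no event rates, so these are an assumed range. Power is the sum, over all pairs of counts (i, j) with two-sided Fisher p ≤ 0.05, of Bin(i; n, p1) × Bin(j; n, p2).

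| Assumed rates | 85 per arm | 100 per arm | 170 per arm |
|---|---|---|---|
| 1% vs 2% | 0.3% | 0.6% | 3% |
| 2% vs 4% | 3% | 4% | 11% |
| 5% vs 10% | 16% | 19% | 34% |
| 5% vs 15% | 52% | 59% | 84% |
| 5% vs 20% | 82% | 88% | 99% |

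At 85 per arm with no events in one arm, five in the other gives p = 0.059 and six gives p = 0.029.

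**Step 4: what would counts and cases add?** The chance of at least one event among n women is 1 − (1 − p)^n. At n = 85 it is 57% for p = 1%, 82% for 2% and 99% for 5%. So cases would probably be available to review even where a test has almost no power.

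Zero events in 85 would put a one-sided 95% upper limit of 1 − 0.05^(1/85) = 3.5% on the rate, but only if loss is unrelated to wound problems. As a purely hypothetical illustration, suppose 15 of 100 women in an arm are not reached and 5 of those had an event. The true proportion is then 5/100 = 5%, with 0 of 85 seen. This is why the number not reached in each arm belongs beside the counts.

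**The case against.** **Pain carries some safety information.** The background connects infection, breakdown and scarring with later pain, and pain is collected at 6 weeks. This stands. But pain does not identify which event occurred, or whether one occurred, so it does not replace counts of the four events.

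**The text does not close off other data.** A reader might infer that the look can cover pain and sexual function only. The document does not support that: it never says what the look analyses, and its list of recorded characteristics is introduced as examples. The list's named items are, however, maternal, pregnancy and birth characteristics, not follow-up outcomes. Wound problems may also surface in routine care, but nothing makes them trial data by arm.

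**The background does not compare these two arms.** This is so. The cited differences involve other suture pairs, and the one monofilament trial is said to have found no difference for most outcomes. The background shows why the events are relevant, not that a difference is expected.

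**Low power limits what the fix can deliver.** This stands for a formal test. At the lower assumed rates the comparison would stay weak even at the end of the trial. The benefit lies in counts and case review.

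**Telephone self-report misses women who are not reached.** This also stands, and is counted as a cost of the fix.

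**Side points.** A reader might see a contradiction between a safety look and "This study does not present any risks to the participants". That sentence can be read as no risk beyond usual care, which is compatible with monitoring. The Statistical Analysis Plan's reference to a 6-week visit, where the methods describe a telephone interview, is a mismatch of wording, and no wound assessment is described under either name. Both should be reconciled, but neither carries weight here.

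**Conclusion.** The point holds in this form: a safety analysis is promised, yet no wound or other adverse event is listed as trial data. Followed as written, neither the look nor the final analysis would have counts by arm of the four wound events that the background links to suture choice. This goes beyond missing detail, because events that are not collected cannot be supplied later by a fuller description of the look. It does not show that the look is confined to pain and sexual function, nor that one suture is less safe than the other.

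The practical size is moderate. The primary comparison is untouched, and what is lost is descriptive safety information. The power figures rest on assumed event rates, on a mid-point at 200 randomised, and on 85 to 100 women per arm at the look because the loss has no stated timing. The conclusion is the same across that range. It is limited to the text available for review.

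**What to change.** 1. Add yes/no questions on wound infection, wound breakdown, re-suturing and suture removal to the 6-week and 3-month calls already planned.
2. Define the mid-point, for example when the first 200 randomised women have reached the 6-week call. At that point review event counts by arm, the individual cases, and the number not reached in each arm.
3. Use one Fisher's exact test, a method the plan already names, on any wound event as support only. Keep the four event types descriptive, and state that the look will have low power.
4. State that pain, dyspareunia and sexual function will not be compared for benefit at the look, and that pain may be reviewed for harm.
5. Report the wound events by arm at the end.

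While editing, state who reviews the look and what it can lead to, and reconcile the risk sentence and the visit or telephone wording.

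**Cost:** four questions on two existing calls, a few sentences in the monitoring section, slightly longer calls and some case-review work. The information will be self-reported, available only for women reached (and loss may be related to wound problems), and weak for formal comparison unless the difference is large.
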